5.4.1.2 Prohibited Medications or Treatments During Study

Medications such as those listed below are not permitted in the course of the trial:

- Concurrent treatment with other investigational drugs
- Concurrent treatment with any other anticancer therapy including radiotherapy

5.4.2 Study Treatment Accountability and Compliance Procedures

Administration of the study treatment will be supervised by the Investigator or sub-Investigator. The study treatment should not be destroyed until the site is contacted by the Sponsor to provide disposition details. The person responsible for drug dispensing is required to maintain adequate records of the study treatment. These records (e.g., product accountability log) include the date the study treatment is received from the Sponsor and administered to the patient.

The person responsible for study treatment administration to the patient will record precisely the date and the time of the study treatment administration.

5.5 Safety and Efficacy Variables and Study Assessments

Flow charts for the study assessments are provided in Table 1.

5.5.1 Pre-study Assessments

5.5.1.1 HAAH expression of archived tissue

After patient consent is given, archived tumor tissue (if available) and serum will be tested for the expression of HAAH. Patients who test positive may be enrolled into the study.

5.5.1.2 HAAH expression in serum

After patient consent is given, patient serum will be tested for the expression of HAAH (Section 7.5.3.2). Patients who test positive will be enrolled into the study.

5.5.2 Study visits and assessments

The following evaluations will be performed. All procedure dates defined are based on the duration (days) from the initial dose of study medication.

5.5.2.1 Screening period (Day -56 (+ 7 days) to Day 0)

Following patient informed consent, archived prostate tumor tissue and patient serum will be tested for the expression of HAAH. Only patients who test positive for HAAH expression in archived tumor tissue (if available) or fresh serum may be continued in the study. If tumor tissue or fresh serum is initially negative for HAAH, the patient can be re-screened for the study if PSA level have increased over the next 6 months, patient is willing to participate on study in the future, and HAAH expression is now positive in serum or tumor tissue (on retest). If archived tumor tissue is negative on initial testing, the same tumor tissue will not be retested.

Assessments at Screening:

- Informed consent administered
- HAAH expression in archived tumor tissue (if available) and/or fresh serum
- Medical/oncology history, demographics
- Baseline signs and symptoms
- Physical examination, vital signs, ECG

- Eastern Cooperative Oncology Group (ECOG) performance score
- Prostate-specific antigen (PSA) assessment: if the screening period is between 3 and 8 weeks prior to first dose, the PSA must be re-tested within 14 days prior to first dose
- Clinical laboratory tests, chemistry, hematology, coagulation, CH50 if the screening period is between 3 and 8 weeks prior to first dose, the labs noted must be re-tested within 14 days prior to first dose
- Pelvic MRI or CT scan in addition to bone scan.

5.5.2.2 Dose-escalation Treatment: Day 1

- Immunologic blood collection pre-dose on day of drug administration (eg Day 1) and 21 days thereafter.
- Medical/oncology history review
- Symptom-directed physical examination
- Prostate-specific antigen (PSA) assessment
- Vital signs, ECG
- ECOG score
- Baseline biochemical testing (chemistry, CBC, coagulation, CH50,) prior to study drug administration
- Study treatment administration
- Physician administration site assessment (post administration)
- Adverse events and concomitant medications

5.5.2.3 Dose-escalation Treatment: Day 8 ± 2 days

- Symptom-directed physical examination
- Vital signs
- ECOG score
- Biochemical testing: chemistry, hematology, coagulation, CH50
- Physician administration site assessment
- Adverse events, concomitant medications

5.5.2.4 Dose-escalation Treatment: Day 15 ± 2 days

- Symptom-directed physical examination
- Vital signs
- ECOG score
- Clinical laboratory tests, chemistry, hematology, coagulation, CH50
- Adverse events, concomitant medications

5.5.2.5 Study Visits: Day 22, Day 43 ± 3 days

- Immunologic blood collection pre-dose on day of drug administration on Day 22, 43, and every 21 days thereafter if continuing treatment
- Symptom-directed physical examination
- Vital signs and ECG
- Eastern Cooperative Oncology Group (ECOG) performance score
- Prostate-specific antigen (PSA) assessment
- Biochemical testing: chemistry, hematology, coagulation, CH50
- Evaluation of subject to allow continued dose escalation
- Study treatment administration
- Physician administration site assessment (post-administration)
- Adverse events and concomitant medications

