| Dose cohorts will be enrolled sequentially and no dose escalation will occur until all patients in the current cohort complete the first 21-day cycle. After the first patient in each cohort has demonstrated adequate safety and tolerability for at least 21 days, the next 2 patients in the cohort may be enrolled. When at least 3 patients have reached Day 21 if none of the first 3 patients experiences a DLT, then dose-escalation to the next level can begin. Multiple patients can be in the screening phase but the first eligible patient able to be treated is assigned the treatment slot that is available for study. |
| A safety assessment of administration site reactions (ASR) will be made by the Investigator at least 30 minutes (or later) following each dose of study drug using the (NCI-CTCAE V4.03). Enrollment will be held if an ASR of grade 3 or greater (NCI-CTCAE V4.03) is observed, until the event resolves. In the event enrollment is held for an ASR, the Sponsor and Investigator will evaluate the outcome of the ASR and must agree to continued enrollment. |
| In patients who tolerate SNS-301, additional treatment may be continued with single doses of SNS-301 at their current dose level, to maintain geometric mean titer (GMT) of HAAH antibodies to no less than 4 times the baseline value for at least six months (9 injections). Treatment will be terminated with the 9th injection or will otherwise be terminated at any time upon the observance of PSA doubling < 90 days or occurrence of unacceptable toxicity. After termination, patients will be followed for an additional 6 months with monthly PSA levels and imaging studies as needed. If an unacceptable rise is detected in the patient's PSA levels following treatment discontinuation, patients shall be eligible for immediate resumption of therapy. |

Г

T

٦

| | Once the MTD/RP2D is determined, patients receiving ongoing treatment may be escalated to that dose for subsequent treatments. These patients will continue to be followed for safety and biochemical PSA monitoring. Pharmacodynamics: Exploratory pharmacodynamic (PD) analysis will be performed using dose, vaccine-specific antibody response (geometric mean of titer), antigen-specific T and B cell indices, and the relative expression of HAAH in each patient's tumor. The PD will be balanced and optimized to the degree of antigen-specific immune response and minimized for the production of |
|---------------------------------|--|

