| | Signs and symptoms (bascline): Screening, Day 1 Physical examination: Screening and end of study (EOS) Symptom-directed physical examination: Day 1, Day 8, Day 15, Day 22, Day 43 and if additional treatment is given, at 21-day intervals thereafter Biochemical testing (chemistry, CBC, coagulation, CH50): Screening, Day 1, Day 22, Day 43 and if additional treatment is given at 21-day intervals thereafter and EOS Biochemical testing (chemistry, CBC, coagulation, CH50) Day 8 and Day 15 during cycle 1 Study treatment administration: Day 1, Day 22, Day 43 and if additional treatment is given, at 21-day intervals thereafter for a total of 9 injections. Patients who have received more than 9 injections due to the timing of the amendment that details limiting therapy to 6 months (9 doses), will be stopped at their last dose received and be followed for 6 months as with other patients. Patients with off-treatment evidence of progression and declining HAAH immune parameters during the 6-month observation period will have the option of immediately resuming therapy on study protocol. Physician administration site assessment: Day 1, Day 8, Day 22, Day 43 and if additional treatment is given at 21-day intervals thereafter; and EOS Safety evaluation of subject to permit continued enrollment in each cohort Day 21 for every first and last patient in a dose level Eastern Cooperative Oncology Group (ECOG) performance score: Screening, Day 1, Day 8, Day 15, Day 22, Day 43 and if additional treatment is given, at 21 day intervals thereafter; and EOS Prostate-specific antigen (PSA) assessment: Screening, Day 1, Day 22, Day 43 and if additional treatment is given, at 21 day intervals thereafter; until injection number 9 (or last dose otherwise) and EOS. Afterwards PSA levels will be obtained on a monthly basis for a total of 6 months. Martue olici blood collection: Screening, Day 1, Day 22, Day 43 and if additional treatment is given, at |
|-----------------------|--|
| Statistical analysis: | No formal statistical analysis will be performed, however, statistical derivation of all data will be derived by dose cohort and displayed for inspection. |

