4.2.2 Secondary

- Incidence of administration site reactions
- Biochemical safety and tolerability
- Geometric mean titers of anti-HAAH antibodies by dose
- Antigen-specific CTL responses by dose
- Production of B cell and T cell response of interest

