5.5.3.3 Administration site reaction

The area around the administration site will be assessed by the physician for adverse reactions at least 30 minutes post study drug administration. The Investigator will grade any ASRs according to the NCI-CTCAE V4.03 (excluding the actual expected micro-injection punctures).

Patients will be required to report any change in the administration site and return to the clinic for evaluation by the Investigator.

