8.6.1 Administration Site Reactions

Administration Site reactions include local (injection site) reactions, such as pain, tenderness, erythema/redness, and swelling. Events are collected via the Physician Administration Site Assessment eCRF page and are graded using a severity rating of 0 (none), and 1, 2, 3, 4 (mild, moderate, severe, potentially life threatening).

A summary of the number and percentage of subjects experiencing at least one administration site reaction anytime after the first study treatment administration will be tabulated by reaction type, maximum severity, and dosage group through Day 43, and separately, for additional treatment visits after Day 43. A separate summary will be tabulated for each visit that an assessment is scheduled.

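### After dose 1, no injection site check is scheduled between dosing visits, and the end-of-study check in the synopsis is missing from the schedules, so delayed reactions may be under-counted

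*Protocol*

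**What the plan says.** Protocol 4.2.2 opens its list of secondary endpoints with "Incidence of administration site reactions". Under study design, the synopsis has the investigator assess the site "at least 30 minutes (or later) following each dose of study drug". Protocol 5.5.3.3 agrees: "The area around the administration site will be assessed by the physician for adverse reactions at least 30 minutes post study drug administration".

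Dose 1 has one more scheduled look, at Day 8 (Protocol 5.5.2.3). From dose 2 onward, Protocol 5.5.2.5 lists "Physician administration site assessment (post-administration" at Days 22 and 43, and 5.5.2.6 gives the same item for every additional treatment visit.

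The documents disagree on what follows the last dose. The synopsis has "Physician administration site assessment: Day 1, Day 8, Day 22, Day 43 and if additional treatment is given at 21-day intervals thereafter; and EOS". Protocol Table 1 and SAP Table 4-1 leave the follow-up/end-of-study cell of that row blank, and none of the eight items in Protocol 5.5.2.7 is a site assessment.

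Between visits, Protocol 5.5.3.3 relies on the patient: "Patients will be required to report any change in the administration site and return to the clinic for evaluation by the Investigator". Protocol 5.5.3.5 adds open-ended adverse event questions at every visit.

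For the analysis, SAP 8.6.1 says "Events are collected via the Physician Administration Site Assessment eCRF page". It plans one summary of subjects with a reaction at any time after first dosing, split at Day 43, and a second summary by scheduled assessment visit.

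**The concern.** Ascertainment of a secondary endpoint is uneven across doses. After dose 1 a structured examination falls about a week later. After doses 2 to 8 the next structured examination comes three weeks later, once a new injection has been given, so a lingering reaction may be hard to tell from a fresh one. After the last dose, a site that follows Table 1 does no later examination, while the synopsis says one is due.

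Reaction rates by visit, and at additional visits where patients may have moved to a higher dose level, therefore partly reflect how closely each dose was observed. Site reactions also carry operational weight: under Protocol 5.2.4 a reaction of grade 3 or above triggers an enrollment hold.

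**Working it through.** The plan states no figure on this point, so the check is a count of scheduled assessments, followed by a trace of the data into the tables.

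**Inputs.** Nine injections, 21 days apart (Protocol 5.1). Site checks as listed in Protocol Table 1, Protocol 5.5.2.2 to 5.5.2.7, the synopsis and SAP Table 4-1.

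**Dosing days.** Dose k falls on Day 1 + 21 × (k − 1): Days 1, 22, 43, 64, 85, 106, 127, 148 and 169.

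**Time from each dose to the next scheduled site check, beyond the check on the dosing day:**

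| Dose | Table 1 and visit lists | Synopsis |
|---|---|---|
| 1 | Day 8: 8 − 1 = 7 days | 7 days |
| 2 to 8 | 21 days, after the next injection | 21 days |
| 9 | none | 28 days, if EOS is the 28-day visit |

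- Total checks for a 9-dose patient: 9 + 1 = 10 under Table 1, and 10 + 1 = 11 under the synopsis.
- Doses with a check between dosing days: 1 of 9 (11%).
- With visit windows, the Day 8 check falls 7 ± 2 = 5 to 9 days after dose 1. The 21-day interval becomes 18 to 24 days at additional visits. From Day 22 to Day 43 it becomes 15 to 27 days (21 ± 6) if both windows are anchored to Day 1. The 28-day visit becomes 25 to 31 days.

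**Illustration.** Assume a reaction begins s days after the dose, with s from 1 to 7, and the patient does not report it. To be visible at a check c days after the dose it must last at least c − s days:

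- dose 1 (c = 7): 0 to 6 days;
- doses 2 to 8 (c = 21): 14 to 20 days;
- dose 9 under the synopsis (c = 28): 21 to 27 days.

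The onset range is an assumption, because the documents give none.

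**What adding EOS alone would do.** It takes the count from 10 to 11 and changes dose 9 only. Doses 2 to 8 stay as they are.

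**Which visit EOS means.** The synopsis entry on study duration places the end-of-study visit 28 days after the last dose. Table 1 and Protocol 5.5.2.7 merge it with six months of 28-day visits. SAP 7.4.5 treats the first follow-up visit and the end-of-study visit as different things.

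**Route into the tables.**

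- SAP 7.4.6 removes a reaction from the adverse event counts when it is also on the site assessment page. No rule works the other way, so a reaction held only in the AE log has no stated route into the site reaction tables.
- SAP 7.4 keeps follow-up assessments in listings unless noted otherwise. The site reaction tables in SAP 10.1 cover visits through Day 43 and additional treatment visits only. An EOS finding would not be tabulated even if it were collected.
- SAP 8.6 assigns additional-visit data to the dose level taken at the visit before, and 8.6.1 states no different rule. The scheduled look follows that day's injection. Read literally, a fresh reaction to a patient's first escalated dose would be tabulated under the earlier, lower dose.

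**The case against.** The strongest reply is that delayed reactions are not left unobserved. Patients must report any change and return for evaluation. Adverse events are asked about at every visit. A symptom-directed examination is listed at every dosing visit, ahead of the injection, and follow-up visits have a complete physical examination and adverse event collection. The first summary in SAP 8.6.1 counts reactions at any time, so an unscheduled entry on the assessment page could be included. The eCRF and the table shells are not part of the documents, so whether the page accepts such entries cannot be seen. Nor do the documents say whether successive injections use the same site; if they do not, old and new reactions are easier to tell apart. Cycle 1, which governs the DLT and MTD decisions, has the Day 8 check.

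All of this stands, and it rules out several stronger readings a reader might infer:

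- That sites go unexamined after later doses, or that the last dose is never examined. Every injection, including the last, has the check at 30 minutes or later.
- That delayed reactions are lost. They have a route into the adverse event data.
- That reaction rates must appear to fall after dose 1. Early reactions are looked for after every dose, so observed rates could rise.
- That the injection-site infiltrates in the rat study (Protocol 3.2) show what later looks would find. They were microscopic and considered non-adverse, and dermal Draize observations were unaffected.

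The reply does not remove the EOS contradiction, the uneven schedule, or the missing link from the AE log to the site reaction tables.

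**Conclusion.** The point holds as a gap in the scheduled ascertainment and tabulation of delayed site reactions. One of nine doses has a site check between dosing days. Seven wait about 21 days for a check that follows a new injection. The last has no later check in Table 1, 5.5.2.7 or SAP Table 4-1, in conflict with the synopsis. The counts assume a patient who receives nine doses on the nominal calendar; if treatment stops early, the same applies to doses 2 up to the second-last, and to the last.

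The supportable consequence is that delayed reactions after dose 1 may be under-counted in the site reaction tables. The size cannot be computed, because the documents give no onset or duration data and patient reporting would recover an unknown share. The DLT and MTD assessment is little affected. The change is worth making because it is cheap and the endpoint is a named secondary.

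**What to change.** 1. Reconcile the synopsis, Protocol Table 1, Protocol 5.5.2.7 and SAP Table 4-1 on the EOS site assessment, and define which visit EOS means. State in SAP 8.6.1 and the SAP 10.1 table list that this visit enters the site reaction tables; otherwise SAP 7.4 leaves it in listings.
2. In Protocol 5.5.2.5, 5.5.2.6 and both schedules, add from Day 22 a brief pre-dose look at the previous site, with recall of any reaction since the last dose (onset, worst grade, resolution). Recall matters because a short reaction will be gone by then.
3. Record between-visit reactions on the same eCRF page, or state in the SAP that site reactions recorded only in the AE log are included in the site reaction tables.
4. In SAP 8.6.1, attribute pre-dose and between-visit findings to the preceding dose, and post-dose findings to that day's dose, in place of the SAP 8.6 default.

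The cost is a few minutes at visits already taking place, a time-point field on the eCRF page, and edits to the schedules and SAP. No new visit is needed. There are two downsides. Observed incidence will be slightly higher. Patients treated after the change will be observed more fully than those treated before it and, since cohorts enroll sequentially, that difference can align with dose. Comparisons by dose should carry a note saying so.

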5.5.2.6 Additional treatment: Every additional 21 days ± 3 days if indicated

A maximum of 9 drug administrations will be administered on this study for all patients, except in the case of progression on study and or in the case of patients who had been on study for more than 6 months at the time of this amendment. Patients with evidence of progression and declining HAAH immune parameters within 6 months of stopping therapy have the option of resuming therapy on the study protocol.

- Immunologic blood collection pre-dose on day of drug administration every 21 days thereafter if continuing treatment.
- Symptom-directed physical examination
- Vital signs and ECG
- Eastern Cooperative Oncology Group (ECOG) performance score
- Prostate-specific antigen (PSA) assessment
- Biochemical testing: chemistry, hematology, coagulation, CH50
- Study treatment administration
- Physician administration site assessment (post-administration)
- Adverse events and concomitant medications

5.5.2.7 Follow up and End of Study (EOS): 28 days \pm 3 days after last treatment for a total of 6 months

- Complete physical examination
- Vital signs
- Eastern Cooperative Oncology Group (ECOG) performance score
- ECG
- Prostate-specific antigen (PSA) assessment
- Clinical laboratory tests, chemistry, hematology, coagulation, CH50 (only on first follow up)
- Immunologic blood collection
- Adverse events and concomitant medications

5.5.3 Safety Measurements

5.5.3.1 Clinical Laboratory Assessments

Hematological toxicities will be assessed in term of hemoglobin value, white blood cell, neutrophil, platelet and, lymphocyte count according to NCI-CTCAE V4.03 AE grading.

Laboratory abnormalities (grade 1 and greater that are listed in the NCI-CTCAE V4.03) should be recorded on the AE page regardless of their causality. Test analytes are provided in the table below.

| Hematology | Serum chemistry |
|---|---|
| Full and differential blood count Hematocrit (Hct) Hemoglobin (Hgb) Platelet count Red blood cell (RBC) count White blood cell (WBC) count with differential | Albumin Alanine aminotransferase (ALT) Aspartate aminotransferase (AST) Alkaline phosphatase (ALP) Blood Urea Nitrogen (BUN) or Urea Carbon dioxide (CO ₂) Creatinine Electrolytes (Na, K, Cl, Ca, P) Glucose (either fasting or non-fasting) Lactate dehydrogenase (LDH) Total bilirubin Direct bilirubin Total cholesterol Triglycerides |

| Coagulation, CH50 | PSA |
|---|-----|
| Prothrombin time (PT)/INR Activated partial thromboplastin time (PTT) | PSA |

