- a HAAH assessment: following informed consent, archived prostate tumor tissue and patient serum will be tested for the expression of HAAH. Only patients who test positive for HAAH expression in archived tumor tissue (if available) or fresh serum may be continued in the study. HAAH assessments are not subject to the 56-day screening window and are valid for 6 months. Patients who are negative for HAAH may be followed for 6 months and if PSA rises over that period time, they can enroll in the study provided that tissue or fresh serum is positive for HAAH
- b Biochemical testing (chemistry, complete blood count, coagulation, and total complement CH50,) to be obtained within 14 days prior to study drug administration if screening period is between 3 and 8 weeks. PSA levels are also to be evaluated at screening and within 14 days prior to study drug administration if screening period is between 3 and 8 weeks.
- c Immunologic blood collection: to be taken pre-dose on the day of study drug administration (Day 1) and every 21 days thereafter. Following the 9th dose (or last dose otherwise), PSA levels and other assessments will be followed on a monthly basis for 6 months. Patients with evidence of progression and declining HAAH immune parameters will have the option of resuming therapy on the study protocol.

- d Baseline radiological tumor burden evaluation consists of a baseline pelvic MRI or CT scan in addition to bone scan. These studies will need to be performed within 56 days (+ 7 days) prior to the start of the study.
- e Patients that have a delay in screening beyond 56-days may be re-screened for randomization.
- f Adverse events that occur post patient receiving study drug. Should Adverse event occur prior to patient receiving study drug they will be captured as Medical History.

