5.5.3.5 Adverse Events (AE)

Adverse event means any untoward medical occurrence associated with the use of a drug in humans, whether or not considered drug related and occurs after the patient is given the first dose of study drug. Any AE that occurs prior to the first dose is part of the medical history.

At least 30 minutes post dose, the Investigator should evaluate the site of drug administration and query the patient in a general manner regarding the presence of any untoward effects.

Laboratory abnormalities (grade 1 and greater that are listed in the NCI-CTCAE V4.03) should be recorded on the AE page regardless of their causality. Worsening of a pre-existing condition is also considered an AE as is the discovery of an abnormal finding during physical exam that was not included in the medical history.

Patients will be encouraged to spontaneously report any AE. Study personnel will ask open-ended questions to obtain information about AEs at every visit. Date and time of onset and resolution (if applicable) of the AE will be documented.

Causality

Events will be considered treatment related if classified by the Investigator as possible, probable, or definitely associated with the use of the drug. Association of events to the study treatment will be made using the following definitions:

| Term | Definition |
|----------------|--|
| Definitely Not | The event is definitely not associated with study treatment. |
| Probably Not | The temporal association, patient history, or clinical condition is such that the study treatment is not likely to have had an association with the observed event. |
| Possible | The event: a) follows a reasonable temporal association with the study treatment administration, but b) could have been produced by the patient's clinical condition or other therapy. |
| Probable | The event: a) follows a reasonable temporal association with the study treatment, b) abates upon discontinuation of study treatment, and c) cannot be reasonably explained by the patient's clinical condition or other therapy. |
| Definite | The event: a) follows a reasonable temporal association with the study treatment, b) abates upon discontinuation of study treatment, c) cannot be reasonably explained by the patient's clinical condition or other therapy, and d) reappears on re-exposure to the study treatment. |

Severity

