7.4.5 Derived Variables

- Non Treatment Emergent Adverse Events include all AEs that stopped the day prior to the first vaccination, started prior to the first vaccination but did not increase in severity or relationship during treatment, or started more than 30 days after *the final study treatment administration* date.
- Treatment Emergent Adverse Events (TEAEs) include all AEs that start on or after the first study treatment administration, or AEs that are present prior to the first administration, but their severity or relationship increases after the first administration up to and including 30 days after the final administration date.
- Change from baseline will be calculated as the observed value at the current visit or time point minus the observed value at baseline.
- Number of doses administered will be calculated for each subject by summing the number of doses administered over all visits.
- *Prior medications* include all medications that have a start date prior to the date of first study treatment administration.
- Concomitant medications include all medications that are taken on or after the date of first study treatment administration.
- The end of treatment phase visit will be the visit immediately after the last visit where treatment was administered. This visit will be the first follow up visit for subjects who have any follow up visits, or the End of Study visit for all other subjects.

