7.4.6 Data Handling

Any administration site reaction found in the AE log that is also captured on the Physician Administration Site Assessment eCRF page will not be counted as an (unsolicited) AE to avoid duplication.

Unscheduled or repeated laboratory results will not be analyzed for the summary of continuous values.

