8.6.3 Laboratory Parameters

Laboratory results will be summarized descriptively for each parameter and dosage group by visit for the observed value as well as for the change from baseline value. Laboratory abnormalities (grade 1 and greater that are listed in the NCI-CTCAE V4.03) will be recorded on the AE page regardless of their causality.

Test analytes are provided in the table below.

Hematology	Serum chemistry
Full and differential blood count	Albumin
Hematocrit (Hct)	Alanine aminotransferase (ALT)
Hemoglobin (Hgb)	Aspartate aminotransferase (AST)
Platelet count	Alkaline phosphatase (ALP)
Red blood cell (RBC) count	Blood Urea Nitrogen (BUN) or Urea
White blood cell (WBC) count with	Carbon dioxide (CO2)
differential	Creatinine
	Electrolytes (Na, K, Cl, Ca, P)
	Glucose (either fasting or non-fasting)
	Lactate dehydrogenase (LDH)
	Total bilirubin
	Direct bilirubin
	Total cholesterol
	Triglycerides
Coagulation, CH50	
Prothrombin time (PT)/INR Activated partial thromboplastin time (PTT)	ALYTICAL

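### A laboratory AE need not be new or worse than baseline, so TEAE counts depend on how sites date carried-in abnormalities, and no planned table sets laboratory grade against baseline

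*Protocol*

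**What the plan says.** **Recording.** Protocol 5.5.3.1 states: "Laboratory abnormalities (grade 1 and greater that are listed in the NCI-CTCAE V4.03) should be recorded on the AE page regardless of their causality". Protocol 5.5.3.5 and 5.5.3.8 and SAP 8.6.3 repeat the rule. None of the four places refers to the baseline grade.

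**Pre-dose findings.** Protocol 5.5.3.5 says: "Any AE that occurs prior to the first dose is part of the medical history". Footnote f to the Time and Events Schedule agrees: "Should Adverse event occur prior to patient receiving study drug they will be captured as Medical History". SAP 7.4.3 leaves medical history uncoded.

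**Treatment emergence.** SAP 7.4.5 counts as treatment-emergent any AE with onset at or after dosing ("TEAEs) include all AEs that start on or after the first study treatment administration"), together with earlier AEs whose severity or relationship increases. It classes as non-treatment-emergent those AEs that "started prior to the first vaccination but did not increase in severity or relationship during treatment".

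**Laboratory tables.** SAP 8.6.3: "Laboratory results will be summarized descriptively for each parameter and dosage group by visit for the observed value as well as for the change from"; the comparison is with the baseline value. SAP 7.4 fixes the statistics as n, median, mean, standard deviation, minimum and maximum. SAP 7.4.6 adds: "Unscheduled or repeated laboratory results will not be analyzed for the summary of continuous values". In the SAP 10.1 table list the laboratory entries are all change-from-baseline tables; the only shift tables are for ECOG and ECG.

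**The concern.** The recording rule and the TEAE rule do not fit together for a laboratory value that was already abnormal at entry. The TEAE exclusion acts on AE records with a pre-dose onset. The protocol sends pre-dose findings to a different form, so the AE log may hold no earlier record for the exclusion to act on. The first on-study panel showing the same unchanged value then has to be recorded, and if it is dated to that visit it is treatment-emergent.

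Patients can enter with abnormal values. The exclusion limits in Protocol 5.2.2 begin at 2.5 × ULN for ALT and AST and at 2 × ULN for total bilirubin, and hemoglobin is excluded only at 9 g/dL or below.

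At stake is the ability to see whether laboratory toxicity rises with dose. Protocol 3.2 reports a slightly prolonged, non-adverse prothrombin time in rats: males at 1 × 10^11 particles and above, and females at 3 × 10^11. These are dose levels planned for this trial. A comparison of baseline grade with worst later grade, by dose, would address that question directly, and none is planned.

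**Working it through.** The plan states no figure on this point, so the check is a trace through the text followed by an illustrative calculation.

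**1. One unchanged abnormality, followed through the rules.** Assume an analyte is Grade 1 at Screening and on Day 1 before dosing, and still Grade 1 on Day 8.

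| How the site handles it | Governing text | Result |
|---|---|---|
| AE record with the true pre-dose onset | SAP 7.4.5, non-treatment-emergent definition | Not a TEAE |
| AE record with Day 8 onset, when first found on study | SAP 7.4.5, first limb of the TEAE definition | TEAE |
| AE record with onset month missing, same year as first dose | SAP 7.4.8 imputes the first-dose date, unless its override to a more conservative date is used | TEAE unless overridden |
| Medical history only, no AE record | Protocol 5.5.3.5 on pre-dose events, against the literal recording rule | Not in the AE tables |

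The patient's biology is the same in all four rows and only the paperwork differs. Programming cannot settle it by matching the AE term to a coded history term, because medical history is uncoded.

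Protocol 5.5.3.5 shows the condition that is missing. It makes an abnormal physical finding an AE only when the medical history does not already contain it. Laboratory values carry no such condition.

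**2. Which outputs are affected.** TEAE incidence by system organ class and preferred term (SAP 8.6.2) can be inflated. The tables in SAP 8.6.3 cannot, because they subtract the baseline defined in SAP 7.4.10.

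**3. Whether another table shows worsening in grade.** SAP 8.6.2 tabulates severity by system organ class, and preferred term by relationship. Neither gives grade by analyte. The laboratory summaries are ungraded and omit unscheduled results. No planned table therefore gives CTCAE grade by analyte against baseline.

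**4. Scale.** Let q be the proportion of patients who enter with at least one graded abnormality that persists. The documents do not give q, so it is assumed here, with patients independent. The chance that a cohort of n contains at least one such patient is 1 − (1 − q)^n.

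| Assumed q | n = 3 | n = 6 | Expected among 18 (18 × q) |
|---|---|---|---|
| 10% | 1 − 0.9^3 = 27% | 1 − 0.9^6 = 47% | 1.8 |
| 30% | 1 − 0.7^3 = 66% | 1 − 0.7^6 = 88% | 5.4 |
| 50% | 1 − 0.5^3 = 88% | 1 − 0.5^6 = 98% | 9.0 |

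These are chances of having a patient at risk of misclassification. They become chances of a misclassified patient only if every such abnormality is dated on study. One patient is 1/3 = 33% of a cohort of 3 and 1/6 = 17% of a cohort of 6, so a single dating choice can move a row of the TEAE table by that much.

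**The case against.** Four points can be made for the plan.

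- A reader might infer that every carried-in abnormality counts as treatment-emergent. The documents do not say so. Protocol 5.5.3.5 adds that "Worsening of a pre-existing condition is also considered an AE", which suggests that an unchanged condition is not one. The same section asks for the date of onset, and the SAP definition plainly expects some AE records with pre-dose onset. This stands: the defect is an outcome left to site practice, not a wrong outcome that the plan defines.
- A reader might infer that the secondary endpoint of biochemical safety is itself distorted. It is not. SAP 6.4 defines it on the laboratory panels, and SAP 8.6.3 summarises those as change from baseline. This stands in full.
- It is tempting to say that visit summaries hide one patient's toxicity. With 3 to 6 patients, the minimum and maximum expose an outlier at a scheduled visit, all data are listed, and unscheduled results are dropped only from the continuous summaries. This mostly stands. What remains is that no table attaches a grade to an analyte or sets it beside the patient's own baseline grade.
- It is also tempting to size the problem by the number of chance out-of-range values across many analytes and visits. Most of those would be new on study, in patients normal at baseline, and would rightly remain TEAEs after any fix. Only persistent carried-in abnormalities are at issue.

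Finally, the trial is small and descriptive, and Protocol 6.1 plans no formal analysis. That limits the severity. It does not remove the ambiguity.

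**Conclusion.** The concern holds as two limited reporting gaps. First, whether an unchanged carried-in laboratory abnormality enters the TEAE tables depends on the onset date the site chooses. Second, no planned table shows laboratory CTCAE grade by analyte against baseline, although ECOG and ECG both get shift tables.

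The size is uncertain because the prevalence of baseline abnormality is not given. At an assumed 10%, about a quarter of cohorts of 3 and nearly half of cohorts of 6 would include a patient at risk; higher prevalence raises both. Actual inflation also depends on how sites date these events, which the documents do not settle.

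The DLT criteria in Protocol 5.3.5.1 do not use TEAE status, so the MTD and RP2D decisions are unaffected. Severity is minor to moderate.

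**What to change.** Keep the recording rule, so that sites need not change practice, and make the comparison in the SAP.

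1. In SAP 7.4.5 and 8.6.3, classify a laboratory AE as treatment-emergent only when its CTCAE grade exceeds the baseline grade. Use the baseline of SAP 7.4.10: Day 1 pre-dose, or Screening if Day 1 is missing. Alternatively, keep every laboratory AE in the tables and flag each as worse or not worse than baseline. The flag suits a sponsor who wants to keep the existing limb under which an increase in relationship makes an event treatment-emergent.
2. Add tables of baseline grade against worst post-baseline grade, by analyte and dosage group, for hematology, chemistry and those coagulation tests that CTCAE grades. Use scheduled and unscheduled results.

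The data are already collected. The cost is SAP wording, one derived flag and a few extra tables. Abnormalities that are new on study would still count, as they should.
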